## I. PURPOSE OF THE STUDY AND BACKGROUND

Cervical cancer is among the most preventable forms of cancer. Implementation of widespread cervical cancer screening has resulted in a tremendous decrease in the incidence of cervical cancer in the United States and stands as a cornerstone of preventive health efforts. Still, only 80.7% of U.S. women aged 21 – 65 years report adherence to U.S. Preventive Services Task Force (USPSTF) cervical cancer screening recommendations. This rate is far below the *Healthy People 2020* target of 93%. The group identified as most likely to be non-adherent with recommended screening protocols are patients who use the emergency department (ED) for their usual source of care. **The overall goal of the proposed study is to pilot two brief behavioral interventions aimed at improving adherence to cervical cancer screening among ED patients.** The results of this pilot will prepare our interdisciplinary team to successfully compete for NIH funding to scale up the evaluation of the proposed interventions. In order to achieve this goal, we propose to leverage an existing parallel service program in the high volume general population setting of the URMC ED to accomplish the following specific aims:

**Specific Aim 1:** Conduct a randomized pilot trial comparing the efficacies of two structured behavioral interventions in promoting adherence of women aged 21 – 65 to USPSTF cervical cancer screening recommendations: A. Screening & referral and, B. Screening, brief mobile technology-based intervention grounded in the Theory of Planned Behavior (TPB), & referral.

**Hypothesis 1A/1B:** The proposed interventions will improve adherence to USPSTF recommendations at follow-up over baseline levels. Rates of adherence will be greater after Intervention B compared to A.

**Specific Aim 2:** Identify predictors of adherence and non-adherence to USPSTF recommendations at baseline to inform the refinement of the proposed interventions.

[figure not shown]
**Hypothesis 2:** Lower baseline rates of adherence will be identified among ethno-racial minorities, as well as among women with less education, without a usual source of care, and with greater barriers to care.

**Specific Aim 3:** Collect qualitative feedback on perceptions of the interventions to inform their refinement.

[figure not shown]

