**Figure 1. Project Workflow**

After consent, enrollees will complete a ~10-minute computer-adaptive questionnaire, administered at the bedside on a tablet computer by the EDRA to determine adherence to current USPSTF recommendations for cervical cancer screening. The REDCap adaptive screening tool used will be identical to that which was used to gather our preliminary data. The enrollment process will categorize study participants into three groups: adherent, uncertain, or non-adherent (Figure 2). Women found to be adherent will be notified and their participation will conclude (i.e. no follow-up will be performed). Women found to be in the uncertain or non-adherent groups will then be randomized into one of two intervention conditions. Randomization will be automated in the REDCap survey instrument. All women found non-adherent will be referred to their usual care provider. If the patient does not have a usual provider of women's healthcare, she will be referred to UR WHP to receive appropriate screening. [name] (co-I) will maintain an expedited referral pathway to UR WHP for these subjects. [name] or one of the other health care providers at WHP will conduct the screening test. Women for whom adherence is uncertain (e.g. unsure, unable to remember) will be referred to their usual care provider or to UR WHP to confirm their adherence status. If, upon follow-up, the patient was confirmed adherent, she will be retroactively classified as adherent at baseline (though her uncertain status at screening will be retained in the dataset for potential secondary analyses). If confirmed non-adherent, the patient will be retroactively classified as non-adherent at baseline (with initial uncertainty retained). If the patient did not contact a provider to confirm adherence status (and did not remember her status in the 150 day interim), she will remain classified as uncertain.

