### **XI. DATA ANALYSIS**

**a. Plan of Analysis.** Based on previous research and our preliminary data, we anticipate  $\geq 18\%$  of patients will be non-adherent to screening guidelines. As such, we will enroll 450 patients to identify  $\geq 90$  non-adherent patients. To test **Specific Aim 1 - Hypotheses 1A/1B**, we will use (a) a one sample test of improvement in adherence at follow-up and (b) a two-sample comparison of post-intervention adherence across intervention conditions. These analyses will allow us to establish preliminary effect sizes for powering the subsequent NIH submission. The first test will compare % adherent at follow-up against a null value of 15% improvement (i.e., % of non-adherent subjects who would become adherent over 150 days without intervention). We think this is an unrealistically high null value, but it was chosen to avoid overestimating the impact of the study interventions. Using this null value, a one-tailed test with  $\alpha=0.05$ , and  $\geq 90$  non-adherent subjects across conditions, we will have power of 0.80 to observe improvement as small as 10% over the null (40% relative improvement). The second test will use  $\chi^2$  to compare conditions. Given a one-tailed test with  $\alpha=0.10$  and 45 non-adherent subjects in each condition, we will have power of 0.70 to observe a difference as small as 24% in adherence at follow-up. More importantly, we will establish a 95% confidence interval around the overall improvement rate (across conditions) with  $\leq 10.4\%$  margin of error and intervention specific rates of improvement with  $\leq 14.8\%$  margin of error. These intervals will allow us to calculate power for the subsequent trial under expected, ideal, and worst-case scenarios. Patients lost to follow-up will be considered intervention failures (i.e. non-adherent) in accordance with intention-to-treat principles. In order to test **Specific Aim 2 - Hypothesis 2**, we will use hierarchical, multinomial logistic regression to predict adherence at baseline. Given our sample size and an expected adherence rate of 0.80, at  $\alpha=0.05$ , we will have power  $\geq 0.70$  to observe odds ratios as small as 1.33. Any covariates demonstrating a  $p$ -value  $\leq 0.10$  will be addressed when refining the interventions for the subsequent NIH trial. **Specific Aim 3** is focused on the qualitative feedback data collected at the 150-day follow-up call. Qualitative data analysis of the feedback data will include open and axial coding under Grounded Theory principles examined in the context of subject demographic characteristics. The codes/concepts that emerge from these data will be examined in the context of the demographic characteristics of the subjects providing feedback. Results will then be used to refine the intervention protocols for the subsequent efficacy trial.

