
**b. Additional Analyses.** Supplemental analyses will be performed in order to strengthen interpretations of potential intervention effects. Specifically, we will perform the analyses described above among only those women who were referred to UR WHP (i.e., those without a usual provider of women's healthcare). Although we are not specifically powering our study around this subset of subjects, these analyses may help us identify success within this underserved population or important covariates/barriers than must be addressed when intervening with subjects lacking a usual women's healthcare provider. We will also corroborate subject self-reports of contact and screening using UR WHP records and subject eRecords (for those with providers associated with UR Medicine) as a way to further validate the findings observed. Finally, we will evaluate over-referral in our study by examining the percentage of women deemed to have uncertain adherence status who are reclassified as adherent, as well as those potential individuals deemed non-adherent in our study who find they are adherent through their women's healthcare providers. This rate of over-referral will be useful when evaluating the impact of the interventions on both subject health and clinical resource utilization.

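### Aim 2's stated power of at least 0.70 at an odds ratio of 1.33 fits a continuous predictor per SD; for the yes/no predictors in Hypothesis 2 the power is at most about 0.23 two-sided or 0.33 one-sided

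*Combined protocol and SAP*

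**What the plan says.** Hypothesis 2 (section I) is mainly a set of group contrasts. It predicts: "Lower baseline rates of adherence will be identified among ethno-racial minorities". It extends this to women with less education and to those "without a usual source of care, and with greater barriers to care".

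Section XI.a plans "hierarchical, multinomial logistic regression to predict adherence at baseline". With the planned sample size, an expected adherence rate of 0.80 and alpha 0.05, it claims power of at least 0.70 "to observe odds ratios as small as 1.33". It does not say whether that odds ratio is per SD, per category or yes versus no. It gives no predictor prevalence and no sidedness, although both Aim 1 power statements in the same section say one-tailed. No other section supplies these details.

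Three related points:

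- **Coding.** The referral rule in section II ("If the patient does not have a usual provider of" women's healthcare, refer to the university practice) and the subgroup in section XI.b ("those without a usual provider of" women's healthcare) already split women yes/no on an item close to the usual-source-of-care predictor.
- **Outcome.** Enrollment will "categorize study participants into three groups: adherent, uncertain, or non-adherent", but the power sentence gives a single adherence rate.
- **Use.** Covariates with p ≤ 0.10 "will be addressed when refining the interventions for the subsequent NIH trial".

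**The concern.** An odds ratio means little for power until its unit is known. One SD of a yes/no variable with prevalence q is √(q(1−q)), which is at most 0.5. A yes-versus-no odds ratio of 1.33 is therefore a much weaker signal than 1.33 per SD. The sentence is offered as the power for testing Hypothesis 2, which names at least two predictors that are naturally yes/no, and nothing limits it to continuous ones.

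At stake is how a null result is read. Someone who takes the sentence at face value could treat a non-significant result for minority status or usual source of care as ruling out an odds ratio of 1.33, and could leave that factor out when the interventions are refined. A sample of 450 cannot support that inference.

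**Working it through.** **Inputs from the plan (XI.a).** n = 450; adherence 0.80, read as the overall rate; alpha 0.05; odds ratio (OR) 1.33; flagging rule p ≤ 0.10. ln(1.33) = 0.2852.

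**Assumptions made here.** Prevalence q of a yes/no predictor is not given, so a range is shown. The exposed group is taken as less adherent, as Hypothesis 2 predicts. The outcome is treated as adherent or not, with one predictor and no correlated covariates.

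**Step 1: reproduce the stated figure (continuous predictor, per SD).**
Power = Φ(√(n·p·(1−p))·ln OR − z) = Φ(√(450 × 0.80 × 0.20) × 0.2852 − z) = Φ(8.485 × 0.2852 − z) = Φ(2.420 − z).

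- Two-sided 0.05 (z = 1.960): Φ(0.460) = 0.677.
- One-sided 0.05 (z = 1.645): Φ(0.775) = 0.781.

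The OR per SD for power 0.70 is exp((z + 0.524)/8.485), which is 1.34 two-sided and 1.29 one-sided. These bracket 1.33, so the plan's figure fits a per-SD odds ratio. Simulation (8,000 runs) gives 0.670 and 0.782.

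**Step 2: yes/no predictor.**
Find adherence p0 (unexposed) and p1 (exposed) such that (1−q)p0 + q·p1 = 0.80 and the odds p0/(1−p0) are 1.33 times the odds p1/(1−p1). Then
var(log OR) = 1/[n(1−q)p0(1−p0)] + 1/[n·q·p1(1−p1)], and power = Φ(ln OR/√var − z).

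Example at q = 0.5: p0 = 0.823, p1 = 0.777, √var = 0.237, ln OR/√var = 1.204. Power is Φ(1.204 − 1.960) = 0.225 two-sided and Φ(1.204 − 1.645) = 0.329 one-sided.

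A one-sided 0.05 test and a two-sided 0.10 test share the same critical value, so they share a column.

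| q | Power at OR 1.33: two-sided 0.05 | one-sided 0.05 or two-sided 0.10 | one-sided 0.10 | OR for power 0.70: two-sided 0.05 | one-sided 0.05 or two-sided 0.10 | one-sided 0.10 |
|---|---|---|---|---|---|---|
| 0.1 | 0.118 | 0.192 | 0.305 | 2.32 | 2.10 | 1.88 |
| 0.2 | 0.172 | 0.264 | 0.394 | 1.95 | 1.80 | 1.64 |
| 0.3 | 0.206 | 0.307 | 0.444 | 1.84 | 1.70 | 1.56 |
| 0.4 | 0.224 | 0.328 | 0.467 | 1.80 | 1.67 | 1.54 |
| 0.5 | 0.225 | 0.329 | 0.469 | 1.82 | 1.68 | 1.54 |

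Over q from 0.02 to 0.98, the maximum power at OR 1.33 is 0.226, 0.331 and 0.471 respectively, at q = 0.46. Simulation (200,000 runs per setting) agrees: at q = 0.5 it gives 0.221, 0.329 and 0.470. A pooled two-proportion test gives maxima of 0.228 two-sided and 0.333 one-sided at 0.05.

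**Step 3: put the two scales side by side.**
An OR of 1.33 per SD corresponds to a yes-versus-no OR of 1.33^(1/√(q(1−q))): 1.77 at q = 0.5 and 2.04 at q = 0.2. At q = 0.5, OR 1.33 means 82.3% v 77.7% adherent, whereas the two-sided detectable OR of 1.82 means 84.7% v 75.3%.

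**Step 4: sample size implied by the claim.**
At q = 0.5, power 0.70 at OR 1.33 needs about (z + 0.524)²/(0.16 × 0.25 × 0.2852²) women. That is roughly 1,900 two-sided or 1,450 one-sided, against 450 planned.

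**The case against.** The strongest reply is that the stated figure is incomplete, not wrong. Read per SD and one-sided, it reproduces at 0.78. One-sided is plausible, since Hypothesis 2 is directional and both Aim 1 tests are one-tailed. The sentence never expressly claims to cover yes/no predictors, and the plan does not say how covariates are coded. Education and barriers to care may be scored, and minority status could be entered as several categories. The ceilings also depend on reading 0.80 as the overall rate. Finally, the plan nowhere says that a non-significant covariate is ruled out, and it gives no expected effect sizes, so 1.33 need not be the yes/no effect that matters.

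Some of this stands. The per-SD reading is accepted, no claim is made about education or barriers, and the harm runs through a reader's inference and not through a rule in the plan. None of it rescues the sentence. The figure is given without limit as the power for Hypothesis 2, which includes group contrasts. Reading 0.80 as the reference group's rate raises the ceilings only to 0.24 and 0.35. Splitting minority status into several categories would not restore the power. The looser p ≤ 0.10 rule leaves power at 0.26-0.33 two-sided (0.39-0.47 one-sided) for prevalences of 20-50%.

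**Conclusion.** The concern holds. The design does not deliver the stated power for the yes/no predictors to which the sentence is applied: at most 0.23 two-sided or 0.33 one-sided at alpha 0.05, against the claimed 0.70. Even at the most favourable prevalence, a true odds ratio of 1.33 would be missed about 77% of the time at two-sided 0.05.

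The result rests on n = 450, overall adherence of 0.80, and a single predictor with a two-category outcome. The ceilings do not depend on prevalence; the detectable odds ratios do. Adjustment for correlated covariates would usually lower power further, and the three-category outcome splits the non-adherent side.

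The consequence is limited. Aim 2 is exploratory, 450 was set for Aim 1, and refinement of the interventions also draws on the follow-up call and Aim 3.

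**What to change.** Restate the Aim 2 power sentence in section XI.a with unit, sidedness and predictor type. For example: *With 450 women and adherence 0.80, at two-sided alpha 0.05, power is about 0.70 for an odds ratio of 1.34 per SD of a continuous predictor, and of about 1.8-2.0 for a yes/no predictor with 20-50% prevalence (about 2.3 at 10%), before any allowance for correlated predictors or a three-category outcome.* If a one-sided test is intended, say so and use 1.29 per SD and about 1.7-1.8 (2.1 at 10%). The prevalences are assumptions, and the investigators should substitute their own where they have them.

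Add one line saying that a yes/no predictor with p > 0.10 is not to be read as evidence of no association at an odds ratio of 1.33.

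The cost is a text edit. Enrollment, model and flagging rule stay as they are; the only downside is a less favourable stated figure for yes/no predictors.

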**b. Description of Interventions.** The proposed study pilots two interventions aimed at improving adherence to guidelines by encouraging screening outside of the ED. **Intervention A** only involves screening for adherence status and referral of uncertain and non-adherent patients for screening and/or confirmation of status and screening. **Intervention B** follows the Screening, Brief Intervention, and Referral to Treatment (SBIRT) model popularized in the substance use literature in the ED . The three components of the TPB intervention will be delivered via a series of text messages to mobile phones. Patients will receive a total of three text messages at 30-day intervals between the ED index visit and telephone follow-up survey at

150 days. Each text message will include a statement directed towards one of the TPB predictors of behavioral change intentions (Table 1) accompanied by a reminder to schedule cervical cancer screening with their primary provider or the WHP. Attitudes regarding cervical cancer screening will be addressed by emphasizing its efficacy for preventing morbidity.

Table 1 – Theory of Planned Behavior Texts to Participants in Intervention B

Element of the TPB	TPB portion of text	Scheduling portion of text
Attitudes about Screening	“Regular screening for cervical cancer is an extremely effective way to prevent cancer or identify early stages of cancer that can be effectively treated”	
Subjective Norms about Screening	“Over 80% of women across the country stay up-to-date with cervical cancer screening guidelines.”	Schedule cervical screening by calling your usual women’s health provider at {Participant-specific phone number} or with UR Women’s Health Practice at [contact]
Perceived Behavioral Control over Obtaining Screening	“Pap tests are available, without cost to you, at your women’s health provider or at the UR Women’s Health Practice.”	

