A limited medical record review will be conducted for all enrolled subjects to determine cervical cancer screening activities and results through providers associated with UR Medicine in the prior 5 years. These data will be compared to self-reported screening activities to demonstrate the validity of the study procedure used in the current study. These data will also be used to determine the extent to which subjects are aware of their suggested screening schedules based on history (e.g., abnormal Pap test results, positive high-risk HPV test).

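### The over-referral rate counts only women whose status is resolved and reported by day 150, so it is probably too low, and the planned record review is not used to fill the gap

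*Combined protocol and SAP*

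**What the plan says.** Over-referral is the last item in Section XI.b (Additional Analyses). The team will "evaluate over-referral in our study by examining the percentage of women deemed to have uncertain adherence status who are reclassified as adherent", and will add women "deemed non-adherent in our study who find they are adherent through their women's healthcare providers". The result is meant to inform the interventions' effect on subjects' health and on clinical resources.

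The reclassification rule is in Section II.a: "If, upon follow-up, the patient was confirmed adherent, she will be retroactively classified as adherent at baseline". The rule for the remaining uncertain women begins "If the patient did not contact a provider to confirm adherence status (and did not remember her status in the 150 day interim), she will" and ends by leaving the woman in the uncertain class. An uncertain woman can therefore be resolved in two ways, by a provider or by her own recall. The non-adherent component is defined through providers alone.

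Classification comes before allocation: "Women found to be in the uncertain or non-adherent groups will then be randomized into one of two intervention conditions". Under Section II.b only Intervention B receives three texts, each "accompanied by a reminder to schedule cervical cancer screening with their primary provider or the WHP". Section II.c collects the outcome by telephone at 150 days, with up to three call attempts.

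Section II.c also states: "A limited medical record review will be conducted for all enrolled subjects". That review covers UR Medicine providers over the prior five years. Its stated purposes are to validate self-report and to assess women's awareness of their screening schedule. Section XI.b uses records to corroborate self-reports, not to resolve women who report nothing. Section XI.a counts women lost to follow-up as non-adherent for Aim 1; no rule is given for over-referral.

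**The concern.** An ED referral was unnecessary if the woman was already up to date when she was screened. That fact precedes randomisation and does not depend on what she does next. The planned measure does depend on it: she must contact a provider or remember her status, and she must answer the call. An up-to-date woman who does none of this cannot enter the numerator. On the natural reading of the percentage for uncertain women, she remains in the denominator.

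Two things are at stake. The rate could make the ED questionnaire look more accurate than it is, which matters when the next trial's referral load is planned. And if someone later tabulated the rate by arm, the arm that prompts more contact would appear to over-refer more, although the referral rule is the same in both.

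**Working it through.** **The plan's own figure.** There is none to reproduce. The documents give no over-referral rate, target or precision, no contact rate and no telephone reach rate. What follows illustrates the mechanism under assumptions.

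**Identity.** With all uncertain women as the denominator and no false confirmations, in each arm:

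observed rate = t × r × c

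where t is the true share already up to date, r the share reached at day 150, and c the share of those reached whose status was resolved.

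**Inputs.** t = 50% and r = 80% are assumptions. For c, two screening-uptake figures from Section XI.a serve as stand-ins: the 15% null value for arm A, and 15% plus the 24-point detectable difference, 39%, for arm B. Section XI.a does not offer these as resolution rates.

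**Base case.**
- A: 0.50 × 0.80 × 0.15 = 6.0%
- B: 0.50 × 0.80 × 0.39 = 15.6%
- Pooled, equal arms: (6.0 + 15.6)/2 = 10.8%, against a true 50% (50/10.8 = 4.6-fold too low)
- Gap between arms with no true difference: 9.6 points

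**Range.** With the same c, t from 30% to 70% and r from 60% to 100%:
- Pooled: 0.30 × 0.60 × 0.27 = 4.9% to 0.70 × 1.00 × 0.27 = 18.9%
- Gap: 0.30 × 0.60 × 0.24 = 4.3 to 0.70 × 1.00 × 0.24 = 16.8 points
- If c is 15% in both arms, the gap is zero and the rate is still too low

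A different set of assumptions (t = 20%, c from 20% to 40%, r from 60% to 80%) gives 0.20 × 0.20 × 0.60 = 2.4% to 0.20 × 0.40 × 0.80 = 6.4%.

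**Adding recall.** Suppose a share q of women without provider contact remember their status, so that c becomes c + (1 − c)q:

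| q | A | B |
|---|---|---|
| 0 | 6.0% | 15.6% |
| 10% | 9.4% | 18.0% |
| 30% | 16.2% | 22.9% |

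Recall shrinks the shortfall and the gap but removes neither.

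**Allowing false reports.** If a share f of reached women who were truly not up to date wrongly report that they were, observed = r × [t × c + (1 − t) × f]. In arm B, f = 10% gives 19.6% and f = 30% gives 27.6%, compared with 15.6%. At a lower true rate the direction can reverse: with t = 20% and f = 30%, 0.80 × (0.20 × 0.39 + 0.80 × 0.30) = 25.4%, above the truth.

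**Using the record review.** If pre-visit records identify a share u of the truly up-to-date women regardless of contact, observed = t × [u + (1 − u) × r × c]:

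| u | A | B | Gap (points) |
|---|---|---|---|
| 0 | 6.0% | 15.6% | 9.6 |
| 30% | 19.2% | 25.9% | 6.7 |
| 60% | 32.4% | 36.2% | 3.8 |
| 90% | 45.6% | 46.6% | 1.0 |

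The documents do not give u.

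**Restricting to resolved women.** This does not repair the rate. With t = 50%, if 20% of up-to-date and 40% of not-up-to-date women are resolved, the figure is 0.10/(0.10 + 0.20) = 33%. With the two shares reversed it is 67%.

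**The case against.** Several stronger readings are tempting, and the documents do not support them.

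- *Provider contact is the only route.* A reader might infer this from Section XI.b, but Section II.a also resolves uncertain women who remember their status. It is true only of the non-adherent component.
- *The plan will make Intervention B look more wasteful.* No comparison by arm is stated. Section XI.b speaks of a single rate for the study. Dependence on arm is a hazard if the rate is split, not a planned error.
- *The rate is certainly understated.* Recall is unverified, and Section II.c seeks no confirmation of screening outside UR Medicine. Understatement follows only if confirmations are accurate.
- *The shortfall has a known size.* Any multiple simply inverts the assumed reach and resolution rates.

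There is also a substantive defence. The plan never defines over-referral as misclassification by the ED tool. For clinic workload, an up-to-date woman who never contacts a clinic costs nothing, so discovered cases are a relevant quantity and more of them in B would partly reflect real extra contact. Confirming status is also part of why uncertain women are referred. This stands, and is a reason to report discovered cases in their own right. It does not make them a measure of how often the tool referred unnecessarily.

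Finally, how unresolved women enter the percentage is partly inference. They keep a separate class, and the non-adherent component has no stated denominator. The record review already planned also bears on the tool's validity. These points reduce the weight of the concern, but Section XI.b still lacks a denominator, a missing-data rule and a link to those records.

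**Conclusion.** The point holds in a limited form. As written, over-referral is ascertained only through provider confirmation or, for uncertain women, recall, reported at day 150. Unresolved and unreached women cannot be counted, and the record review of all enrolled women is not used to resolve them. The rate is therefore likely to be too low, provided confirmations are accurate. It would vary with arm only if reported by arm and if B's reminders raise resolution.

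The size cannot be derived from the documents. With no recall and no false reports, the shortfall is several-fold under the inputs assumed above; recall reduces it, and enough false reporting could reverse it.

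This is minor. The analysis is supplemental, in a pilot, with no hypothesis, power statement or decision rule attached, and nothing in Aim 1 or the sample size changes.

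**What to change.** Amend Section XI.b as follows.

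1. Take all referred women, uncertain and non-adherent, pooled across arms, as the denominator.
2. Count as over-referred those whose UR Medicine record dated before the ED visit shows they were up to date, plus those confirmed adherent at follow-up.
3. Report the number unresolved, and give a lower bound (unresolved counted as not over-referred) and an upper bound (unresolved counted as over-referred).
4. Report provider-discovered cases separately as a measure of resource use, not as the ED tool's over-referral rate.

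Do not restrict the denominator to women with a UR Medicine screening history or to resolved women; both groups are selected.

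The cost is a few lines of text and one variable derived from records already being reviewed. It must be derived before identifiers are deleted at the end of follow-up (Section V.a). The drawback is that records cover UR Medicine only, so the bounds may be wide. In the base case with u = 60%, and with not-up-to-date women resolved as often as the others, the lower bound is 0.50 × (0.60 + 0.40 × 0.80 × 0.27) = 34.3% and the upper bound is 1 − 0.50 × 0.80 × 0.27 = 89.2%. That width shows how much the study would leave unknown, which a single percentage would hide.
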